### In patients with relapsed CLL

- In patients in whom the first line therapy was well tolerated and remission exceeded 24 months, the usual recommendation is to reinstitute the same treatment.
- o In all the other cases (including the patients with the 17p mutation), ibrutinib as a single agent is recommended (Byrd, Jones et al. 2014). The combination of idelalisib and rituximab is an option for patients for whom rituximab alone would not be considered as appropriate therapy due to other comorbidities. Patients may also be considered for clinical trials.

Despite these advances, major challenges persist:

- The available treatments do not eradicate CLL. This issue is especially critical in in patients with poor prognostic factors such as unmutated IGHV and in young patients.
- In the first line setting, the FCR regimen is difficult to use in many patients due to toxicity, so
  there is a need to identify alternative treatments that are as effective but less toxic.
- o Ibrutinib has definite activity but CR is rare. The probability that ibrutinib will eradicate the disease is low, and selection of resistant mutants may result in an escape to ibrutinib therapy.

There is a need to identify more active agents and combinations. One avenue of great interest is to restore immuno-surveillance, and NKG2A blockade by IPH2201 could be one way to achieve this goal.

CONFIDENTIAL

Release date: Edition number 12 August 2016

GED version

MOD-3783

[figure not shown]

CONFIDENTIAL

Release date: Edition number 12 August 2016

GED version

CONFIDENTIAL

Release date: Edition number 12 August 2016 Amendment n° 5 Protocol V5.0 MOD-3783

GED version

#### 1.2.4 Benefits and risks

#### 1.2.4.1 Benefits

Based on the above considerations, the present study aims at inducing MRD negative CR (Byrd, Jones et al. 2014). Achieving such deep responses could provide substantial benefit to patients:

- A delay in the time to occurrence of acquired BTK and PLCγ2 mutations
- A lower rate of disease-related complications (e.g. infections and auto-immune complications)
- A prolongation of PFS and OS

#### 1.2.4.2 Risks

Both drugs, IPH2201 and ibrutinib, are individually well tolerated, and their respective mechanisms of action indicate no particular theoretical safety risk when administered in combination. Several precautionary measures will further limit the risks for participating patients:

#### Trial design

The initial tested dose (1 mg/kg) is 10 times lower than the highest dose (10 mg/kg) tested and proven to be safe in the phase I trial of IPH2201.

During the dose escalation part of the study, IPH2201 will be given as a single drug for 2 cycles over a total of 28 days. Dose-escalation will be based on a review by the safety committee of the data from all patients of the *current* cohort, after they have completed 2 cycles of single agent IPH2201. Introduction of ibrutinib at a new dose level will be allowed by the safety committee after review of the data from all patients of the *previous* cohort, after they have completed 2 cycles of IPH2201 in combination with ibrutinib.

### · Prevention of the lysis syndrome

No tumor lysis syndrome (TLS) has been reported in patient treated by ibrutinib alone (Byrd, Furman et al. 2013). A very limited risk of TLS is expected with IPH2201 administered as single agent given the dysfunction of NK cells and the low immunogenicity of CLL cells. However, literature data suggest that CLL is associated with an intermediate risk of TLS in patients with CLL treated with targeted and / or biological therapies (Cairo, Coiffier et al. 2010). Therefore, adequate prevention and monitoring of TLS will be adopted for the 2 first administrations of IPH2201 as well as for the 2 first administrations of the combination of IPH2201 + ibrutinib in every patient in the dose-escalation phase, including hydration, administration of allopurinol, and clinical and biochemical monitoring.

CONFIDENTIAL

Release date: Edition number

GED version

#### · Patient selection

All provisions of the ibrutinib FDA label will be applied for the selection of patients for the present study (for instance, patients treated with anti-vitamin K will be excluded) (Byrd, Jones et al. 2014). In addition, patients will be excluded if they have a history of auto-immune diseases, including immunologic cytopenia. Patients with CLL in relapse after allogeneic HCT will be excluded.

# · Safety Committee

Dose escalation will be overseen by a safety committee. The safety committee will also review all available data (safety, pharmacology and anti-leukemic activity) to select the dose of IPH2201 for the phase IIa part. The safety committee may decide to prematurely stop the dose escalation, even if the MTD was not reached. The safety committee may also recommend a dosage decrease after the occurrence of 2 unacceptable reactions to the combination of IPH2201 and ibrutinib. Finally, the committee will review the safety data or at any time if a major safety issue occurred during the progression of the trial.

Release date: Edition number

GED version

# 2 STUDY / TRIAL OBJECTIVES AND PURPOSE

### 2.1 PRIMARY OBJECTIVES

Phase lb

The primary objective of the phase Ib is to assess the safety of IPH2201 given IV as a single agent and in combination with ibrutinib in patients with relapsed, refractory or previously untreated chronic lymphocytic leukemia.

Phase IIa

The primary objective of the phase IIa is to evaluate the anti-leukemic activity of the combination of IPH2201 and ibrutinib in patients with relapsed, efractory or previously untreated chronic lymphocytic leukemia.

# 2.2 SECONDARY OBJECTIVES

The secondary objectives are:

- · Phase Ib
  - 1. To determine the PK and PD of IPH2201 given concomitantly with ibrutinib, and to confirm the PK/PD relationship of IPH2201
  - To document the anti-leukemic activity of the combination of IPH2201 and ibrutinib
- Phase IIa
  - 1. To assess the safety of the combination of IPH2201 and ibrutinib
  - 2. To determine the PK and PD of IPH2201 given concomitantly with ibrutinib, and to confirm the PK/PD relationship of IPH2201

Release date: Edition number

GED version

# 3 STUDY DESIGN

### 3.1 STUDY ENDPOINTS

# 3.1.1 Primary Endpoints

Part 1: phase lb

The primary endpoint will be the safety of 2 repeated administrations of IPH2201 given as a single agent during 4 weeks and, thereafter, given in combination with ibrutinib during 52 weeks:

- Occurrence of DLT and identification, if any, of the MTD, during the administration of IPH2201 as a single agent and given in combination with ibrutinib
- Occurrence of AEs and SAEs

Safety will be assessed using the CTCAE version 4.03, apart from neutropenia and thrombocytopenia which severity will be graded by using the IWCLL grading scale reported in appendix IV. It will include a descriptive analysis of the frequency and severity of AEs, as well as clinical laboratory tests collected to assess lab abnormalities, results of vital sign measurements, electrocardiograms (ECGs), physical examinations and imaging studies. Related AEs will be followed to resolution (≤ grade 1) unless deemed irreversible.

Part 2: phase IIa

The primary endpoint will be the rate of complete response, achieved with a combination of IPH2201 and ibrutinib, assessed 52 weeks after the beginning of the treatment, defined according to the guidelines of IWCLL (Hallek, Cheson et al. 2008), and confirmed by a bone marrow biopsy.

# 3.1.2 Secondary endpoints

Part 1: phase lb

0

Secondary endpoints are:

- Rate of overall and complete or partial response defined according to the IWCLL guidelines with an additional category of "PR with lymphocytosis" achieved with IPH2201 given as a single agent during 2 cycles, and, thereafter, with the combination of IPH2201 and ibrutinib, and assessed 52 weeks after the initiation of the combined treatment and during the in-study follow-up period.
- Duration of response, PFS and OS. Progression is defined according to the IWCLL guidelines
- with the exception that lymphocytosis cannot be used as the sole criterion for disease progression
- Pharmacokinetic endpoints
  - Concentration at the end (Cinf end) of the 1st to 4th administrations of IPH2201 (every 2 weeks) and thereafter, every at the end of every other administration (every 8 weeks)
  - Accumulation index in terms of Cmax ratio, between 1st administration and selected later administrations
  - Area under the curve from 0 time to 14 days at the 1st (IPH2201 administered alone) and 3rd (IPH2201 and ibrutinib) administrations for patients in the dose escalation phase

CONFIDENTIAL

[figure not shown]
Release date: Edition number

MOD-3783

12 August 2016

GED version

Terminal half-life (T1/2) and clearance (CL) for patients who will complete the study

Secondary endpoints are:

- Rate of complete response defined according to the IWCLL guidelines, documented during the in-study follow-up period of the study.
- o Rate of overall and partial response defined according to the IWCLL guidelines with an additional category of "partial response with lymphocytosis"
- 0
- o Duration of response, progression-free survival (PFS) and overall survival (OS); progression is defined according to the IWCLL guidelines with the exception that lymphocytosis cannot be used as the sole criterion for disease progression
- o Safety of IPH2201: will be assessed using the CTCAE version 4.03 (descriptive analysis of frequency and severity of adverse events); related adverse events followed to resolution (grade ≤ 1) unless deemed irreversible. Safety evaluation will also be based on clinical laboratory tests collected to assess lab abnormalities, as well as results of vital sign

measurements, electrocardiograms (ECGs), physical examinations and imaging studies.

The following endpoints are optional in the phase IIa part of the study

- Pharmacokinetic endpoints
  - Concentration at the end (Cinf end) of the 1st, 2nd and 4th administrations and thereafter-at the end of every other administration (every 8 weeks).
  - Accumulation index in terms of Cmax ratio, between 1st administration and selected later administrations.

CONFIDENTIAL

Release date: Edition number

12 August 2016 MOD-3783

## 3.2 OVERALL DESIGN

This is a multicenter, open label, single arm Phase lb/IIa study, consisting of 2 parts:

- A part 1 dose escalation phase Ib to confirm the safety of IPH2201 as a single agent during 4 weeks and thereafter combined with ibrutinib during 52 weeks
- A part 2 single-arm phase IIa assessment of IPH2201 combined with ibrutinib during 52 weeks
   36 to 45 patients will be enrolled in this clinical study:
  - 12 to 24 patients (3 to 6 patients at each dose level) will be enrolled in the dose-escalation phase lb
  - o Up to 24 patients in the phase IIa

The last 3 to 6 patients treated during the phase Ib with the IPH2201 recommended dose level for the phase IIa (in principle 10 mg/kg) will be included in the efficacy analysis set of the phase IIa part.

If 6 patients (3+3 for safety reasons) are treated during the phase Ib with the IPH2201 recommended dose level for the phase IIa, a maximum of 21 patients will be included in the phase IIa.

If 24 patients were enrolled in the phase Ib of the trial (including 6 at the IPH2201 recommended dose level for the phase IIa), no more than 21 patients would need to be enrolled in the phase IIa. Therefore, the total number of patients will never exceed 45 (24+21).

[figure not shown]

Release date: Edition number

GED version

# Overall Study Scheme

### 3.3 Administration / Dosage

- o In the part 1 (dose escalation phase Ib) corresponding to the first 12 to 24 patients, IPH2201 is administered as a single agent during the first 2 administrations, at week 0 and week 2; ibrutinib is introduced as a combination therapy from 3rd administration, at week 4.
- o In the part 2 (phase IIa) corresponding to the patients treated at the dose selected by the safety committee, both drugs are administered on the same day from the beginning of the phase IIa, at week 0. On the days scheduled for both IPH2201 and ibrutinib therapy, IPH2201 is administered first, followed by ibrutinib, after end of IPH2201 perfusion.
- o In both parts of the trial, the first 4 administrations of IPH2201 (from week 0 to week 6) occur every 2 weeks. From the 5th administration IPH2201 is administered every 4 weeks.
- Both IPH2201 and ibrutinib may be administered on an outpatient basis
- Treatment by IPH2201 is limited to 56 weeks, or less in the event of a CR with undetectable minimal residual disease documented for 2 months
- Treatment by ibrutinib at least is administered until the end of the follow-up period unless a disease progression (IWCLL), untoward toxicity, or consent withdrawal leads to the premature interruption of the treatment. Patients will be followed 12 months after interruption of IPH2201 treatment

#### CONFIDENTIAL

Release date: Edition number

GED version

### 3.3.1 IPH2201

IPH2201 is administered as a 60-minute intravenous (IV) infusion starting on week 0, day 1 visit. No pre-medication is to be given at 1st administration to avoid masking the potential risk of infusion reactions. However, from the 2nd administration, pre-medication with acetaminophen or anti-histamines may be prescribed at the investigator's discretion if the patient experienced any Grade 1 - 3 infusion-related AE during the previous cycle.

### Part 1: phase lb

In the part 1, dose escalation phase Ib of the trial, 4 doses are planned to be assessed if MTD is not previously reached:

Dose level 1: 1 mg/kg Dose level 2: 2 mg/kg Dose level 3: 4 mg/kg Dose level 4: 10mg/kg

At each of the explored dose levels, a period of at least 7 days must be respected between the first IPH2201 administration of the first treated patient and the first IPH2201 administration of the following patients.

In the part 2, phase IIa of the clinical trial, the doses of IPH2201 will be selected by the safety committee.

Intra-patient dose escalation is not allowed.

In case of any grade ≥3 adverse event:

- Treatment will be temporarily suspended for one week
- Treatment will be resumed at the same dosage in case of resolution to a grade 2 or lower
- In the absence of resolution to a grade 2 or lower, the treatment suspension will be prolonged by 1 more week
- In the absence of resolution to a grade 2 or lower after a 2-week suspension, the patient will be taken off study
- In case of recurrence of a grade 3 related reaction after a temporary suspension, the same suspension will apply, but after resolution to a grade 2 or lower, treatment will be resumed at the lower dose level

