### IPH2201 re-dosing criteria:

- Absence of progression or clinical deterioration
- Absence of grade 4 treatment-related non-hematologic AE following the previous administration
- Resolution of grade 3 or higher adverse event to grade 2 or lower

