3.3.2 Ibrutinib

Ibrutinib will be administered according to the FDA-approved label, i.e., at the dose of 420 mg (three 140 mg capsules) orally once daily. Ibrutinib will be supplied commercially.

In the part 1, phase Ib of the clinical trial, ibrutinib will be administered starting at 3rd administration of IPH2201 at week 4, in the absence of unacceptable toxicity.

In the part 2, phase IIa of the clinical trial, both drugs will be administered on the same day, from the 1st administration and from the beginning of the phase IIa at week 0.

[figure not shown]
Adverse events (AEs): interrupt ibrutinib therapy for any grade  $\geq 3$  or greater non hematological AEs, grade  $\geq 3$  neutropenia with infection or fever or grade 4 hematological toxicities. Once the symptoms of the toxicity have resolved to grade 1 or baseline (recovery), ibrutinib may be reinitiated at the starting dose. If the toxicity reoccurs and persists or after discontinuation of IPH2201, reduce dose by one capsule (140 mg per day). A second reduction of dose by 140 mg may be considered as needed. If these toxicities persist or recur following 2 dose reductions, discontinue ibrutinib. For patients with mild liver impairment (Child-Pugh class A), the recommended dose is 140 mg daily (one capsule).

Concomitant medications: strong CYP3A inhibitors (see appendix V) are contra-indicated if they should be given more than 7 days. If a strong CYP3A inhibitor should be given 7 days or less consider interrupting ibrutinib until the CYP3A inhibitor is no longer needed.—If a moderate inhibitor (see appendix V) should be given for any time period, reduce ibrutinib dose to 140 mg. Strong CYP3A inducers (see appendix V) should be avoided with ibrutinib.

Elective procedures: stop ibrutinib 3 days before and after a minor procedure (e.g. invasive exploration such as a colonoscopy) and 7 days before and after a major procedure (e.g. surgery).

In case of ibrutinib treatment discontinuation, the continuation of IPH2201 treatment is left to investigator's discretion at the same dosage and schedule as before ibrutinib discontinuation.

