#### 9.3 SAFETY COMMITTEE

A safety committee will be constituted to monitor data and overall safety in this study in order to determine the dose to be administered to the patients after phase lb.

The safety committee will consist of:

- The principal investigators of the study
- A sponsor medical and pharmacologist representative
- The sub-investigators as optional members, including the Director of the division of Hematology at OSU as hematologist with high experience in CLL
- A methodologist or physicians with relevant expertise related to the reviewed safety issues can
  join the safety committee as optional member

The Safety Committee will review the data for progression and safety with data collected as following:

- During the dose escalation phase Ib of the trial, at each dose level after the completion of the 2 cycles of IPH2201 by the *last* patient of the cohort
- o During phase Ib, at each dose level the safety committee will also review patients data after completion of 2 cycles of IPH2201 in combination with ibrutinib by the *last* patient of the cohort
- o Furthermore, at any time during the phase lb, considering any additional safety information, the safety committee may decide to decrease the dose of IPH2201 to a lower dose level
- During the phase IIa of the trial, every six months
- The Safety Committee could also be involved at any time should a major safety issue occur.

The functions of the safety committee are multiple:

- To analyze the causality of the AEs in phase Ib
- At each dose level, to allow dose escalation as above described
- To select the dose of IPH2201 which will be assessed during the phase IIa, taking into account all the safety, pharmacology and anti-leukemia activity data gathered at each dose level, with a minimum of follow-up of 4 weeks after the introduction of ibrutinib, in the last patient enrolled in the dose escalation study. Such a dose may correspond to the MTD, to the highest tested dose level or to a lower dose level, chosen during or at the end of the dose escalation. The safety committee may therefore decide to stop prematurely the dose escalation, even if the MTD was not reached. The report of the safety committee will be forwarded to the FDA

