- To recommend the discontinuation of the study, transiently or permanently, or a decrease in the dose, after the occurrence of 2 unacceptable reactions in patients treated by the combination of IPH2201 and ibrutinib during the first or second phase of the study

DLTs and unacceptable reactions are defined as:

- Any grade 3 or grade 4 non hematologic toxicity
- o Grade 4 neutropenia (ANC < 500/μI) lasting ≥7 days after discontinuation of therapy in patients with pre-treatment ANC ≥ 1,000/μI
- o Grade 4 thrombocytopenia (platelet count <20,000/μl and/or ≥75% decrease from pre-treatment value)
- Grade 3 or 4 thrombocytopenia associated with bleeding
- Any dose delay due to AE for > 14 consecutive days

Such events will be considered as DLTs whenever they occurred during the first 4 cycles (8 weeks) of treatment in phase Ib (including 2 administrations of treatment with IPH2201 alone and 2 administrations of treatment with IPH2201 + ibrutinib).

Release date: Edition number

GED version

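### Protocol 3.3.1 ties the IPH2201 dose reduction to a grade 3 recurrence only, so read literally a related grade 4 hematologic event that recurs at grade 4 resumes at the same dose

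*Protocol*

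**What the plan says.** Protocol section 3.3.1 gives one list for phase Ib and a parallel one for phase IIa. Each opens with "In case of any grade ≥3 adverse event". IPH2201 is suspended for 1 week (Ib) or 2 weeks (IIa), and the suspension may be doubled. The default on recovery is "Treatment will be resumed at the same dosage in case of resolution to a grade 2 or lower". Without recovery by 2 weeks (Ib) or 4 weeks (IIa) the patient goes off study.

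The last bullet, worded identically in both lists, is the only patient-level rule that lowers the IPH2201 dose. It begins "In case of recurrence of a grade 3 related reaction after a temporary suspension, the same suspension will apply" and then sends the patient to the lower dose level.

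The re-dosing criteria in the synopsis and the retreatment criteria in section 3.3.3 add three conditions: no progression or clinical deterioration, any event of grade 3 or higher back to grade 2 or lower, and "Absence of grade 4 treatment-related non-hematologic AE following the previous administration". The synopsis text on IPH2201 treatment modifications contains no reduction rule.

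**The concern.** The list is opened by grade 3 or worse, but the reduction bullet names grade 3 alone. The protocol marks the difference elsewhere: section 3.3.3 speaks of grade 3 or higher for resolution, section 4.3 separates grade 3 from grade 4, and section 9.3 names both grades for non-hematologic toxicity. The last bullet also adds its own qualifier, relatedness, so it can be read as a deliberately narrower trigger than the heading.

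On that reading the more severe recurrence gets the weaker dose action. The re-dosing bar closes the gap for non-hematologic grade 4 events but leaves hematologic ones open. At stake is the dosing safety of an individual patient under a rule that sites apply directly. The statistical design is not involved.

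**Working it through.** No figure in the plan is being recomputed, so the check is a trace through the rules, followed by an illustration.

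**Trace for a related event that recurs after an earlier suspension**

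| Recurrent event | Re-dosing bar (3.3.3) | Reduction bullet (3.3.1), literal | Result |
|---|---|---|---|
| Grade 3, resolved in time | no bar on grade | applies | lower dose level |
| Grade 4 non-hematologic | barred | not reached | no re-dosing |
| Grade 4 hematologic, earlier event also grade 4, resolved in time | no bar on grade | does not apply | same dose |
| Grade 4 hematologic, earlier event grade 3, resolved in time | no bar on grade | arguably applies | lower level on that reading |
| Grade 4 hematologic, not resolved in time | – | – | off study |

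The third row is the gap. It assumes no progression and no clinical deterioration. With grade ≥3 in the bullet, the third and fourth rows both give the lower level.

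**Illustration with neutrophil counts**

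The grades follow the Appendix IV table and the grade 4 limit in section 9.3 (below 500/µL). My assumptions are a baseline ANC of at least 1,000/µL, a low count lasting 5 days, and a value recorded as an adverse event.

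- Recurrence at 700/µL: between 500 and 1,000, so grade 3. The bullet applies and the dose is reduced.
- Recurrence at 400/µL after an earlier grade 4 event, recovering to 1,100/µL: 400 is below 500, so grade 4, and 1,100 lies between 1,000 and 1,500, so grade 2. Literally, the same dose is resumed.

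**Does the list of unacceptable reactions in section 9.3 catch the second case?**

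- Grade 4 neutropenia is listed only when "lasting ≥7 days after discontinuation of therapy in patients with pre-treatment ANC" of at least 1,000/µL. Here 5 < 7 days, so it is not listed.
- Also listed: "Any dose delay due to AE for > 14 consecutive days". The first suspension is 7 days (Ib) or 14 days (IIa), and neither exceeds 14. The longest permitted suspension is 14 days in Ib, still not over 14, and 28 days in IIa, which would be listed.
- Grade 4 thrombocytopenia is itself on the list, so it counts toward the two reactions that allow the committee to act.

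**Size of the dose step at issue**

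The levels are 1, 2, 4 and 10 mg/kg. From 10 to 4: (10 − 4)/10 = 60% lower. From 4 to 2: (4 − 2)/4 = 50%. From 2 to 1: (2 − 1)/2 = 50%. Section 3.2 expects 10 mg/kg in principle for phase IIa. These figures describe dose spacing and do not measure harm.

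**The case against.** The strongest reply is that nobody would apply the bullet this way. It sits under a heading for grade 3 or worse and refers back to the suspension that the heading triggers, so a clinician would not read it as sparing a worse recurrence. That is a fair account of the likely intent. It supports calling this a wording slip, but it does not make the written rule right.

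Second, a grade 3 reaction that comes back at grade 4 can be read as a recurrence of a grade 3 reaction. This stands, and it narrows the gap to grade 4 recurring at grade 4.

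Third, other protection exists. A reader might infer that such a patient is left without safeguards, and the documents do not support that:

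- Section 4.3 lets the physician remove a patient after a grade 3 or 4 event and lists the investigator's decision as a separate ground. Section 3.3.3 permits retreatment and does not require it.
- Section 3.3.2 interrupts ibrutinib for, among others, grade 3 or worse "neutropenia with infection or fever or grade 4 hematological toxicities", and restart needs recovery to grade 1 or baseline. If toxicity reoccurs and persists, ibrutinib is reduced by 140 mg, with a possible second reduction and then discontinuation. A brief episode may not meet the persistence condition.
- Section 9.3 says that in phase Ib "the safety committee may decide to decrease the dose of IPH2201 to a lower dose level". It also allows the committee to be involved at any time for a major safety issue, in either phase, and to recommend a dose decrease or discontinuation after two unacceptable reactions.

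All of this stands as mitigation, but none of it sets that patient's IPH2201 dose.

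Fourth, a reader might infer that every recurrent ANC of 700/µL must be reduced. That is too strong. Under sections 9.1.2 and 9.1.4 a laboratory abnormality is normally recorded as an adverse event only if it meets one of the listed conditions, such as symptoms, corrective treatment, a treatment change or seriousness. An ANC of 700/µL without infection or fever does not trigger ibrutinib interruption and may never enter the algorithm. Scheduled hematology is also only every 4 weeks from week 8 (sections 6.2.1.5 and 6.2.2.5), so a 5-day duration would be established only through repeat tests.

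**Conclusion.** The point holds in a narrow form. As written, a related grade 4 hematologic adverse event that recurs at grade 4 and resolves to grade 2 or lower within 2 weeks (phase Ib) or 4 weeks (phase IIa), without progression or clinical deterioration, has no mandatory IPH2201 reduction, while a recurrent related grade 3 event does. The probable cause is a missing ≥. A loss of the sign when the PDF was read cannot be fully excluded, but the bullet appears twice without it while both list headings kept theirs.

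The documents give no frequency for such recurrences. The conditions are restrictive enough that very few patients, possibly none, would be affected. A reader might infer that all grade 4 recurrences escape the rule, or that the efficacy result is at risk. Neither follows: non-hematologic grade 4 events are barred from re-dosing, and alpha, power, the complete response endpoint and the SAP tables do not depend on this bullet. It is worth correcting because it is an operative dosing instruction and the correction is almost free.

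**What to change.** In the last bullet of both lists in section 3.3.1 (phase Ib and phase IIa), change the trigger from a grade 3 related reaction to a grade ≥3 related reaction. Keep the bar on re-dosing after related grade 4 non-hematologic events in the synopsis and section 3.3.3. No synopsis change is needed.

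The cost is one character in each of two bullets, with no new data or procedures. The downside is that a few patients may be reduced who would otherwise have stayed at the same dose.

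An optional clarification, separate from this point, is to state in the same bullet what happens when no lower level exists, that is, for patients assigned or already reduced to 1 mg/kg. Stopping IPH2201 is one choice; the sponsor may prefer another.
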